### 5.4. Examination of Covariates, Other Strata and Subgroups

#### 5.4.1. Covariates and Other Strata

The list of covariates which will be used in descriptive summaries and statistical analyses., including the primary analysis are described in the table below. Additional covariates percent predicted FEV1 and baseline BMI will be explored as a sensitivity analysis for the primary endpoint of the leg press strength only.

Category	Details
Covariates	Treatment, Day, Treatment x Day and Baseline
Exploratory covariates	Percent Predicted FEV1 and Baseline BMI

#### 5.4.2. Examination of Subgroups

There is no subgroup analysis planned for this RAP, however, males and females will be analysed separately since they have a different dose level.

### 5.5. Multiple Comparisons and Multiplicity

The primary comparison of interests is the change from baseline and percent change from baseline in maximum leg press strength following 1 repetition maximum (1- RM). The key endpoint used for decision making purpose will be the percent change from baseline in maximum leg press strength. This analysis will be conducted separately for each gender and the two analyses will be considered co-primary (i.e. both must be considered a success for the study to be successful), therefore no multiplicity adjustment is required. There will be no multiplicity adjustments for multiple endpoints or multiple timepoints or multiple treatment comparisons. Analyses of other efficacy endpoints will not be subject to any multiplicity adjustment.

### 5.6. Other Considerations for Data Analyses and Data Handling Conventions

Other considerations for data analyses and data handling conventions are outlined in the appendices:

Section	Component
12.3	Appendix 3 : Assessment Windows
12.4	Appendix 4 : Study Phases
12.5	Appendix 5 : Data Display Standards & Handling Conventions
12.6	Appendix 6 : Derived and Transformed Data
12.7	Appendix 7 : Reporting Standards for Missing Data
12.8	Appendix 8 : Values of Potential Clinical Importance

## 6. STUDY POPULATION ANALYSES

### 6.1. Overview of Planned Study Population Analyses

The study population analyses will be mainly based on the All Participants population unless otherwise specified.

Study population analyses including analyses of subject's disposition, protocol deviations, demographic and baseline characteristics, prior and concomitant medications, and exposure and treatment compliance will be based on GSK Core Data Standards. Details of the planned displays are presented in [Appendix 11](#): List of Data Displays.

[Table 2](#) provides an overview of the planned study population analyses, with full details of data displays being presented in [Appendix 11](#): List of Data Displays.

**Table 2 Overview of Planned Study Population Analyses**

Display Type	Data Display's Generated	
	Table	Listing
Randomisation		
Randomisation		Y 
Subject Disposition		
Subjects Enrolled by Country and Site ID 	Y	Y
History of Rescreened Subjects 		Y
Reasons for Screen Failure 	Y	Y
Subjects for Whom the Treatment Blind was Broken		Y
Subject Disposition	Y	Y
Study Visit Dates		Y
Populations Analysed		
Study Populations 	Y	Y
Protocol deviations		
Important Protocol Deviations	Y	Y
Deviations leading to exclusion from PP	Y	Y
Inclusion and Exclusion Criteria Deviations		Y
Demography		
Demographic Characteristics 	Y	Y
Summary of Age Ranges 	Y	
Race & Racial Combinations 	Y	Y
Disease Staging		Y
Medical Conditions, Concomitant Medications		
Medical Conditions (Current and Past)	Y	Y

Exacerbation History		Y
Alcohol History		Y
History of Tobacco Use		Y
Change of Smoking Status During the Study		Y
Concomitant Medications	Y	Y
HIV, Hepatitis B and C screening (Hepatitis C viral RNA PCR if Hepatitis C screening is positive)		Y
Other		
IP Compliance 	Y	Y

**NOTES:**

- Y = Display Generated, T = Tables, L = Listings, IP = Investigational Product
1. One listing of subjects randomised but not treated.
  2. Screened population.
  3. Age, sex, age group, ethnicity, race, weight, height, body surface area, percent predicted FEV1 and BMI (kg/m^2) needs to be summarized.
  4. The five-high level FDA race categories and designated Asian subcategories will be summarised along with all combinations of high-level categories which exist in the data. A by-subject listing of race will also be produced.
  5. Dispensation information (dates, number of tablets dispensed, returned, taken and lost, compliance percentage, duration of treatment and treatment cumulative dose also will be included).
  6. Enrolled population

## 7. EFFICACY ANALYSES

### 7.1. Primary Efficacy Analyses

#### 7.1.1. Summary Measure

The adjusted mean treatment difference for change and percent change from baseline in maximum leg press strength will be presented at Days 28, 56 and 90.

#### 7.1.2. Endpoint / Variables

The primary endpoints are change from baseline and percent change from baseline in maximum leg press strength following 1 repetition maximum (1- RM). The key endpoint used for decision making purpose will be the percent change from baseline in maximum leg press strength.

#### 7.1.3. Population of Interest

The primary efficacy analyses will be based on the Analysis population. A supportive efficacy analyses will be based on the Per Protocol population.

#### 7.1.4. Statistical Analyses / Methods

Details of the planned displays are provided in [Appendix 11](#): List of Data Displays and will be based on GSK data standards and statistical principles.

Unless otherwise specified, endpoints / variables defined in [Section 7.1.1](#) will be summarised using descriptive statistics, graphically presented (where appropriate) and listed.

##### 7.1.4.1. Statistical Methodology Specification

Endpoints / Variables

 
• % change from baseline and change from baseline in maximum leg press strength (Kg) following 1 repetition maximum (1- RM) at Days 28, 56 and 90.
 

Model Specification

 
• Change from baseline and percent change from baseline strength will be analyzed separately using mixed models repeated measures (MMRM) adjusted for treatment, day, treatment x day, and baseline strength, with day as the repeated factor.
 
• Data falling into the analysis windows for day 28, day 56 and day 90 will be included in the model
 
• The Kenward and Roger method for approximating the denominator degrees of freedom and correcting for bias in the estimated variance-covariance of the fixed effects will be used.
 
• An unstructured covariance structure for the R matrix will be used by specifying 'type=UN' on the REPEATED line.
 
• In the event that this model fails to converge, the model will be re-fitted with other covariance structures such as compound symmetry and one which gives the least Akaike's Information Criteria (AIC) from the fitted model will be used as the covariance structure.
 
• The analysis will be conducted separately by gender
 

 
If there are any departures from the distributional assumptions for change or percentage change from baseline, the change of log-transformed data at post- baseline from log baseline will be the response variable, adjusted for treatment, log-transformed baseline strength, day and the interaction of treatment and day, with day as the repeated factor. The sensitivity analysis for the change from baseline and percentage change from baseline are the same.
 

Model Checking & Diagnostics

 
Refer to Appendix 9: Model Checking and Diagnostics for Statistical Analyses.
 

Model Results Presentation


 
For change and percent change from baseline, adjusted means, corresponding standard error of means (SEs) and 90% confidence intervals will be presented for each treatment by day, together with estimated treatment differences (GSK2881078 – Placebo) and the corresponding 90% confidence intervals and p-value by day for both Analysis and Per Protocol population.
 
A line plot of the adjusted mean of change (and percentage change) from baseline as well as the 90% confidence interval over time (day) for each treatment from the MMRM model will be provided for the analysis population.
 
 
Log-transformed data results presentation
 
 
The estimated coefficients of the MMRM model will be transformed back (exponential transform).
 
For each treatment, adjusted ratio of the post baseline value to the baseline value and corresponding 90% confidence intervals will be presented by day.
 
The adjusted treatment ratio of the ratio (postbaseline value/baseline value) between the two treatments with the corresponding 90% confidence interval be presented by day.
 
The plot of adjusted ratio of the post baseline value to the baseline value and its 90% confidence interval over time (day) for each treatment arm will be presented for the analysis population
 

Supportive Statistical Analysis - Bayesian

 
% change from baseline in maximum leg press strength following 1 repetition maximum (1-RM) at Days 28, 56 and 90 will be estimated by Bayesian analysis and separately by gender.
 
The posterior probability of treatment difference greater than 4% points, less than 9% points and greater than or equal to 9% points for each visit separately by gender.
 

Model Specification


 
Create indicator variables for the categorical effect: Treatment (GSK2881078 vs. Placebo) and Day (day28, day56 and day90). For treatment, if treatment=placebo, then drug=0; if treatment=GSK2881078, then drug=1;
 
Construct a linear model for each day(visit) in order to model within-subject observation covariance structures by multivariate normal (MVN) distribution in the MCMC procedure. For subject i on treatment j at Day k, the model can be written as: <math>PCH_{ijk} = \beta_0 + \beta_1 \text{ drug} + \beta_2 \text{ baseline} + \beta_d \text{ Day}_k + \beta_{dk} \text{ drug} * \text{Day}_k + \epsilon_{ijk}</math>     <math>\epsilon_{ijk} \sim N(0, \sigma^2)</math>; where PCH refers to percentage change from baseline and Dayk for k=1, 2, 3 represent days 28, 56 and 90, respectively, and are indicator variables, which are intrinsically formed within
 


PROC MCMC from the design matrix. The last element, Day3, is excluded by setting it to 0 in the PARMS statement.
 
 
• <math>(\beta_1 + \beta_{d1})</math>, <math>(\beta_1 + \beta_{d2})</math>, are the estimated treatment differences (GSK2881078 vs. Placebo) at Day 28, Day 56 respectively. <math>\beta_1</math> is the estimated treatment difference (GSK2881078 vs. placebo) at Day 90
 
• Reformat the input data in the way that all repeated measurements from a subject are in one row
 
• Set seed=123456 with the simulation size of 500000, 5000 burn-in iterations. The simulation size and number of burn-in iterations could be updated during the convergence check.
 
• The non-informative priors (normal (0, var=1e6)) will be used for the regression parameters
 
• The 3-dimension inverse wishart scale matrix will be used as the prior of the covariance matrix. The degrees of freedom will be 3 and the positive definite scale matrix will be an identity matrix.
 
• Multivariate normal (MVN) distribution will be specified to model all repeated measurements
 
• Count the proportion at Day90 where <math>\beta_1</math> greater than 4% points, less than 9% points and greater or equal to 9% points respectively from the posterior probability distribution simulation.
 
• Similarly, Count the proportion at Day28 and Day56 where <math>(\beta_1 + \beta_{d1})</math>, <math>(\beta_1 + \beta_{d2})</math> are separately greater than 4% points, less than 9% points and greater or equal to 9% points respectively from the posterior probability distribution.
 
• For calculating the posterior adjusted least square mean and corresponding difference, use the coefficient of L-matrix of the covariates from the MMRM analysis mentioned in Section 7.1.4.1
 

Model Checking & Diagnostics

 
• Refer to Appendix 9: Model Checking and Diagnostics for Statistical Analyses.
 

Model Results Presentation


 
• n, posterior adjusted least square mean and 90% highest posterior density (HPD) interval, the adjusted treatment difference and its 90% HPD credible interval and standard deviation for the posterior adjusted least square mean and difference.
 
• The treatment difference (GSK2881078 – Placebo) for the percentage change from baseline at each visit (Day 28, Day 56 and Day 90) > 4 percentage points, <9 percentage points and <math>\geq 9</math> percentage points will be reported based upon the simulation results from the posterior probability model.
 

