10.3.1. Efficacy Analyses

Endpoint	Statistical Analysis Methods
Primary	
Strength
 
Change from baseline and percent change from baseline strength will be analyzed separately using mixed models repeated measures(MMRM) models with effects for treatment, day, treatment x day, and baseline strength. Differences in least squares means between the GSK2881078 treated group and placebo will be calculated (i.e.; GSK2881078- placebo) along with associated 90% CIs.
 
The same model will be used at both the interim analysis and at the end of the study. The analyses will be performed using all available data from participants in both the AP and the Per Protocol Population. The effects of potential predictors of response including, but not limited to, baseline vitamin D levels and measures of pulmonary function may also be explored.
 
At the interim, the posterior predictive distribution for % change from baseline strength will be estimated. This distribution will be used to estimate the probability that the end of study treatment difference will be $\geq 9\%$. Similarly, at study completion, the posterior distribution will be estimated and used to estimate the probability that the true treatment difference is $\geq 9\%$.
 
Because % change endpoints often demonstrate a lack of normality, a supportive analysis will be performed where log-transformed strength is considered the dependent variable and log-transformed baseline the covariate using a MMRM model as described above. Differences in least squares means between each GSK2881078 treated group and placebo (i.e.; GSK2881078- placebo) along with associated 90% CIs will be constructed. The point estimates and CIs will be back-transformed (exponentiated) to provide point estimates and CIs for the ratios, GSK2881078 to Placebo.
 
Model and distributional assumptions underlying each analysis will be assessed by visual inspection of residual plots. Parameters will be log-transformed prior to analysis if necessary to meet assumptions. If assumptions are still not met after log-transformation alternative methods of analysis will be considered.
 
Complete details will be provided in the RAP. Any changes to the planned analyses described here will be documented in the study RAP and/or the Clinical Study Report.

Exploratory	Will be described in the reporting and analysis plan

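### The strength MMRM and its Bayesian counterpart hold the baseline slope constant over Days 28, 56 and 90, and no planned analysis relaxes this; a baseline x day term would be cheap protection for the Day 90 result

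*SAP*

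**What the plan says.** SAP 7.1.4.1 fits change and percent change in leg press strength, separately by sex, using "mixed models repeated measures (MMRM) adjusted for treatment, day, treatment x day, and baseline strength, with day as the repeated factor". The covariate table in SAP 5.4.1 lists "Treatment, Day, Treatment x Day and Baseline", and Protocol 10.3.1 describes "models with effects for treatment, day, treatment x day, and baseline strength". None includes baseline x day. The covariance is free: "An unstructured covariance structure for the R matrix will be used by specifying 'type=UN' on the REPEATED line".

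The supportive Bayesian section of SAP 7.1.4.1 begins "Construct a linear model for each day(visit) in order to model within-subject observation covariance structures by multivariate normal (MVN) distribution", but the equation that follows has one baseline coefficient, beta2, with no visit index. From that model beta1 "is the estimated treatment difference (GSK2881078 vs. placebo) at Day 90", and its posterior gives P(>= 9). On priors: "The non-informative priors (normal (0, var=1e6)) will be used for the regression parameters".

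The planned variations leave the baseline term alone. SAP 5.4.1 adds percent predicted FEV1 and BMI, SAP 7.3.4.2 drops one centre, and the log-scale fallback in 7.1.4.1 again has a single (log) baseline term. The model checks in SAP 12.9 are residual plots, which would not reliably show a slope that differs by visit.

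**The concern.** Percent change in leg press strength is the key decision endpoint (SAP 5.5 and 7.1.2), judged at Day 90 against 9 points in each sex, with about 20 evaluable participants per arm. The equal-slope restriction is not justified anywhere, and there are reasons to doubt it. Percent change has baseline in its denominator (SAP 12.6.1), the home programme raises the load progressively (Protocol 9.2.5), and strength is expected to be near plateau only by 13 weeks (Protocol 5.4). These make a changing baseline relation plausible; they do not show that one exists.

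If the Day 90 slope differs from the pooled slope, chance baseline imbalance is not correctly removed from the Day 90 comparison. Participants who stop treatment return for safety assessments only (Protocol 8.1, 8.2), and missing values are not imputed (Protocol 10.2). The likelihood analysis then leans on a correct mean model, including the baseline term.

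The Bayesian text also needs clarifying: a linear model per visit suggests visit-specific slopes, whereas an unindexed beta2 says the opposite.

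**Working it through.** **1. The plan's own precision.** Protocol 10.1.1 gives SD 10.9 and 90% half-widths of 8.45 (n = 10 per arm) and 5.8 (n = 20). With t(0.95, 2n-2) x SD x sqrt(2/n): 1.734 x 10.9 x sqrt(2/10) = 8.45, and 1.686 x 10.9 x sqrt(2/20) = 5.81. Both reproduce.

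**2. What the pooled slope is.** With complete data, saturated treatment x day and one baseline slope, the fitted slope is the sum of w_k b_k. Here b_k is the slope at visit k, S is the residual covariance and w = S^-1 1 / (1' S^-1 1). The documents give neither visit SDs nor correlations, so those below are assumptions.

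| SDs at Days 28/56/90 | Correlation | Weights at Days 28/56/90 |
|---|---|---|
| 10.9/10.9/10.9 | compound symmetry | 0.33/0.33/0.33 |
| 10.9/10.9/10.9 | AR(1), 0.5 | 0.40/0.20/0.40 |
| 9/10/10.9 | compound symmetry, 0.5 | 0.50/0.31/0.19 |
| 7.5/9.5/10.9 | compound symmetry, 0.5 | 0.68/0.24/0.08 |
| 7/9/10.5 | 0.65 to 0.80 | 0.95/0.05/-0.01 |
| 12/11.5/10.9 | compound symmetry, 0.5 | 0.26/0.32/0.42 |

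With 25/22/20 per arm observed (assumed) and equal SDs, the Day 28 weight is 0.41 to 0.50. Day 28 dominates only when the SD rises by visit.

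**3. Effect on the Day 90 difference.** The estimate is the raw Day 90 difference minus pooled slope x baseline imbalance. Its displacement is (Day 90 slope - pooled slope) x imbalance. One standard error of imbalance, in baseline SDs, is sqrt(2/25) = 0.28 or sqrt(2/20) = 0.32.

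Assume the Day 90 correlation of percent change with baseline is -0.3 or -0.5. The Day 90 slope is then -0.3 x 10.9 = -3.27 or -0.5 x 10.9 = -5.45 points per baseline SD. Assume also Day 28 and Day 56 slopes at 50% and 75% of that, residual correlation 0.6, and 20 per arm. P is evaluated at an observed difference of exactly 9, as Phi(shift/SE). The SE is 10.9 x sqrt(1 - r^2) x sqrt(2/20), which is 3.29 for r = -0.3 and 2.99 for r = -0.5.

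| SDs | r | Pooled slope | Slope gap | Shift, 1 SE imbalance | P(>= 9), from 0.50 |
|---|---|---|---|---|---|
| equal | -0.3 | -2.52 | 0.75 | 0.24 | 0.53 |
| equal | -0.5 | -4.42 | 1.03 | 0.33 | 0.54 |
| 7.5/9.5/10.9 | -0.3 | -1.87 | 1.40 | 0.44 | 0.55 |
| 7.5/9.5/10.9 | -0.5 | -3.23 | 2.22 | 0.70 | 0.59 |
| 5.5/8/10.9 | -0.5 | -2.63 | 2.82 | 0.89 | 0.62 |

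Equal slopes give a shift of 0. A smaller gap of 0.35 gives 0.35 x 0.28 = 0.10, hence the range of about 0.1 to 0.9. The regression priors are diffuse, so the same displacement carries into the posterior.

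**4. Complete-data simulation** (1,500 trials per scenario, 20 per arm, unstructured covariance estimated, true difference 9). Mean estimates were 8.8 to 9.2 under both models, so neither is biased on average. With equal slopes the SE was 3.30 under both; with diverging slopes the visit-specific model was up to 7% tighter. Within a trial the two Day 90 estimates differed by a median of 0.1 to 0.75 points, and P(>= 9) by a median of 0.01 to 0.06 (95th percentile 0.06 to 0.25).

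**5. Dropout simulation** (800 trials per scenario, 25 per arm, covariance known, SDs 7/9/10.5, about 20 to 25% missing at Day 90, weaker participants more likely to leave). If they leave mainly from the active arm, the common-slope estimate is biased by about -0.5 to -1.2 points; visit-specific slopes give near 0. Slopes of -1/-2.5/-4 per baseline SD give a common-slope RMSE about 2% larger, and -1/-3/-6 about 9% larger with non-differential dropout. With truly equal slopes the common-slope RMSE is 0.983 to 0.996 of the visit-specific one, so the extra term costs 0.4 to 1.7%.

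**The case against.** A common baseline slope is a legitimate, parsimonious prespecification with about 20 evaluable participants per arm and sex, and it matches the protocol. Material harm needs slopes that diverge by visit together with either chance imbalance or arm-dependent dropout, and the documents establish none of these. The listed withdrawal triggers (exacerbation, liver and QTc criteria, personal or investigator choice) give no reason to expect weaker participants to leave mainly from the active arm. The steepest simulated case also exceeds the plan's own variability: a slope of -6 with residual SD 10.5 implies a total SD of sqrt(10.5^2 + 6^2) = 12.1, not 10.9. The change in P is shown where it is most sensitive. At an observed 13 with SE 3.3, a 0.9-point shift moves P only from 0.89 to 0.93. No probability cut-off is visible, so no altered decision can be shown.

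All of this stands and limits the size of the point. It does not supply an analysis that tests the restriction, and it does not settle what beta2 means.

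A reader might infer that the Day 90 result is adjusted mostly with the Day 28 slope. The specification does not imply that. It would hold if the SD of percent change rose clearly by visit; with equal SDs Day 28 carries no more weight than Day 90 under compound symmetry or AR(1) with complete data, and with falling SDs Day 90 carries the most.

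**Conclusion.** The restriction is certain from the text: one baseline slope for three visits in both models, with no planned relaxation. Its consequence is conditional. If slopes differ by visit, the Day 90 difference typically moves by 0.1 to 0.9 points for a one-standard-error imbalance, against a half-width of 5.8. If baseline-related dropout also differs by arm, there is a bias of roughly 0.5 to 1.2 points, the upper end needing steep slopes. With complete 1:1 data there is no average bias, so the documents do not support calling the planned estimate biased as it stands. Visit SDs, correlations, slopes and dropout patterns are all assumed here. This is an improvement to consider, not a flaw that undermines the primary analysis.

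**What to change.** Before the randomisation codes are released for the final analysis:

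- In SAP 5.4.1 and 7.1.4.1, add baseline strength x day to the percent-change and kg MMRMs, and log baseline x day to the log-scale fallback.
- In the Bayesian model, replace beta2 with visit-specific coefficients beta2k, so that the equation agrees with the stated intention to "Construct a linear model for each day(visit) in order to model within-subject observation covariance structures".
- Apply the same term to the multi-visit secondary MMRMs in SAP 7.2.4.1 that reuse this model (lean mass, SPPB measures, PROactive, CAT). No effect size was worked out for these; the reason is consistency.
- Record the change and its rationale in SAP Table 1, since it departs from Protocol 10.3.1.

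If the sponsor prefers to keep the protocol model as primary, the minimum is to prespecify the baseline x day model as a sensitivity analysis and state whether beta2 is common or visit-specific.

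Cost: SAP wording, two extra parameters per sex in each model, and about 0 to 2% larger RMSE if the slopes are truly equal.
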